14.5 Safety Analyses

Adverse events will be monitored during the trial and the data analyzed with respect to incidence within each parent trial treatment group as well as severity and potential relationship of the AEs to investigational drug.

All AEs with a start date before the first dose date in RPC01-3102, which are ongoing from a previous trial to RPC01-3102, will be listed in the AE data listing and labeled as “Prior Adverse Event.”

Adverse events with an onset date on or after the first open-label dose date in RPC01-3102, or with onset prior to the first open-label dose date in RPC01-3102 that increase in severity on or after the first dose of investigational drug will be considered treatment emergent. Treatment-emergent AEs will be summarized for the Safety population by System Organ Class and Preferred Term and presented in descending order of frequency within each System Organ Class. Serious AEs and AEs leading to discontinuation will be summarized similarly.

Associated laboratory parameters such as hepatic profile, renal function, and hematology values will be grouped and presented together. For each laboratory test, individual patient values outside the standard reference range will be flagged and listed. Shift tables will be produced showing the frequency of shifts from Baseline to the highest and to the lowest on-trial value in and out of the normal range as well as by visit. Changes from Baseline to each visit for each numeric laboratory parameter will also be summarized.

The change from Baseline to each visit for each of the vital sign variables will be summarized. Abnormal vital sign values will be flagged and listed.

The change from Baseline to each visit for each of the ECG parameters will be summarized. An outlier analysis of ECG results will be conducted.

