All safety data will be listed and summarized. All TEAEs will be coded and tabulated by System Organ Class and Preferred Term. Incidence of TEAEs, SAEs, AEs leading to discontinuation, and AEs of special interest will be summarized and presented in descending order of frequency. Associated clinical laboratory parameters such as hepatic enzymes, renal function, and hematology values will be grouped and presented together. Individual patient values will be listed and values outside of the standard reference range will be flagged. Shift tables and analyses of changes from Baseline will be produced. The change from Baseline for each of the vital signs and ECG parameters will be summarized. Incidence of abnormal vital signs parameters and outlier ECG results will be tabulated.

Sample Size Justification:

As this is an open-label extension trial for patients who previously participated in a trial of RPC1063 for UC, there is no statistical basis for the sample size. It is anticipated that up to [REDACTED] patients who participated in prior studies of RPC1063 in UC may be eligible for treatment in this trial.

Version and Date: Version 10.0 dated 10 August 2022

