8.3.2 Trial Visits

Visits, assessments, and procedures will be performed according to the Schedule of Events ([Table 2](#)).

Adult patients who are not in clinical response or remission at trial entry may be discontinued from investigational drug if they do not show clinical improvement from the Baseline Visit of the RPC01-3102 by [REDACTED]

At the time this amendment is approved, patients who have completed 5 years of treatment (Week 238) should come in at the time of their next scheduled visit. At this visit, these patients will complete the [REDACTED] procedures and then enter the SFU period.

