13.2.5 Reporting of Serious Adverse Events

Reporting requirements for SAEs will be managed on behalf of the Sponsor by the CRO. Full details of the procedures to be adopted will be documented in a safety management plan approved by responsible parties, in brief:

The Investigator will report any SAE that occurs to any patient from the time written informed consent is signed through the last visit. If an SAE occurs after informed consent and is resolved before the first dose of investigational drug in RPC01-3102, the event will be captured in the parent trial only (eg, RPC01-3101 or RPC01-202). If the SAE is ongoing at the time of the first dose in RPC01-3102, it will be transcribed into the eCRF for RPC01-3102. If an SAE occurs after the first dose of investigational drug in RPC01-3102, it will be captured in the eCRF for RPC01-3102. All SAEs that occur within 90 days of the last dose of treatment with the investigational drug, whether or not considered related to the investigational drug, must also be reported. Any SAE that is ongoing when the patient completes the trial or discontinues from the trial will be followed by the Investigator until the event has resolved, stabilized, or returned to Baseline status.

Any AE considered serious by the Investigator or Sub-investigator or that meets serious criteria should be reported to the CRO's Pharmacovigilance group using the designated SAE reporting forms as well as eCRF forms and procedures. Data entry must be completed within 24 hours from the time the trial site personnel first learned of the event.

The SAE hotline contacts are as follows:

[contact]

[contact]

Email: [contact]

The initial report should be promptly followed by detailed, written reports, which will include copies of hospital case records, discharge summaries, autopsy reports, and other documents when requested and applicable. For unrelated cases, a full detailed case description may negate the need for additional hospital case records, discharge summaries, etc.

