14.2 Statistical Methods

14.2.1 General Considerations

All efficacy and safety data will be listed by patient. Baseline is defined as the last observed measurement prior to the Day █ receipt of investigational drug.

In general, descriptive summaries will be presented for the efficacy and safety variables collected. Continuous variables will be summarized using number of patients (n), mean, standard deviation (SD), minimum, median, and maximum. Categorical variables will be summarized using frequency counts and percentages.

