14.2.2 Analysis Populations

All patients who receive at least one dose of investigational drug will comprise both the Intent-to-Treat (ITT) population and the Safety population. These populations will be used to summarize all efficacy and safety data, respectively.

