14.3 Disposition, Demographics, and Baseline Characteristics

The number and percentage of patients in each population will be summarized. Patient disposition, including the number of patients screened, dosed, and not completing trial by reason for dropout will be summarized. Patient demographics will be summarized and will include age, sex, race, ethnicity, height, weight, and body mass index.

Baseline characteristics for each patient from their previous trial will be summarized and will include age at UC symptom onset, age at UC diagnosis, years since UC symptom onset, years since UC diagnosis, prior anti-tumor necrosis factor use, prior corticosteroid use, each component of the Mayo score, the complete Mayo score, the partial Mayo score, and the 9-Point Mayo score.

Compliance with investigational drug will be summarized and will include the number of patients estimated to be < 80% compliant, 80 to 100% compliant, > 100%, and > 120% compliant.

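### Adverse events are to be reported only as crude percentages, with no exposure summary and no rate per patient-year, although treatment ranges from one dose to Week 238 or beyond

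*Combined protocol and SAP*

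**What the plan says.** Section 14.5 plans to have "the data analyzed with respect to incidence within each parent trial treatment group as well as severity and potential relationship" to investigational drug. It continues: "Treatment-emergent AEs will be summarized for the Safety population by System Organ Class and Preferred Term". SAEs and AEs leading to discontinuation are handled in the same way. The Statistical Methods part of the synopsis agrees: "Incidence of TEAEs, SAEs, AEs leading to discontinuation, and AEs of special interest will be summarized and presented in descending order of frequency". Section 14.2.1 sets the general form of summary: "Categorical variables will be summarized using frequency counts and percentages".

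The denominator is the Safety population of Section 14.2.2: "All patients who receive at least one dose of investigational drug will comprise both" it and the Intent-to-Treat population. The only summary of drug use in Section 14 is in Section 14.3: "Compliance with investigational drug will be summarized and will include the number of patients estimated" to fall in each compliance band. That is the share of doses taken, not time on drug.

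Section 8.3.6 sets treatment to 5 years (Week 238). Section 8.3.2 provides for people already at that point when the amendment is approved: "patients who have completed 5 years of treatment (Week 238) should come in at the time of their next scheduled visit". Sections 8.1 and 8.3.2 allow adults who enter without response or remission to be stopped if they do not improve. Section 8.3.4 allows transfer to commercial drug.

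Section 14.5 defines a treatment-emergent AE (TEAE) by its onset or worsening after the first dose in this trial and gives no end date. Section 13.2.4 has AEs recorded up to the last trial visit, and Section 13.2.5 extends reporting to "All SAEs that occur within 90 days of the last dose of treatment with the investigational drug".

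**The concern.** Long-term safety is the first objective listed in Section 7.1. The percentage of patients with an event rises with time observed, so it can be read as risk only when follow-up is similar across the patients and groups displayed. Here it need not be. The early exits can depend on disease status at entry and on country, and both may differ between parent-trial groups.

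Three readings are affected:

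- **Parent groups side by side.** Section 14.5 chooses this display, but the plan does not show each group's exposure. Groups at equal risk will show different percentages if their mean exposure differs.
- **Pooled figures against parent-trial periods.** One percentage over mixed follow-up cannot be set against a percentage from a period of another length.
- **Change with time on drug.** One percentage cannot show whether risk rises or falls over the years, which is a main reason to run an extension.

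The open-ended TEAE definition adds to this. Off-drug follow-up events enter the same percentage, and off-drug time is a larger share of observation for those who stop early.

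**Working it through.** The plan states no AE rate, exposure or patient-year figure, so there is no stated result to reproduce. The sample size is redacted and has no statistical basis (Section 14.1). The check is a reading of the text followed by an illustration.

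**1. Text.** The synopsis, Section 7.3 and Sections 14.1 to 14.6 contain no person-time denominator, time-to-first-event summary, AE table by period or summary of treatment duration. Section 14.5 gives by-visit summaries for laboratory values, vital signs and ECG, but not for AEs.

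**2. Range of follow-up.** The minimum is one dose (Section 14.2.2). Week 238 is 238 × 7 / 365.25 = 4.56 years if counted from the first dose in this trial. Five years would be 5 × 365.25 / 7 = 260.9 weeks, so the documents' pairing of 5 years with Week 238 depends on what time is counted. From the estimated first enrolment (August 2015) to the date of Version 10.0 (10 August 2022) is about 7.0 years. That is an inferred upper limit at that date, not a reported exposure.

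**3. Equal risk, unequal exposure.** Assume a constant event rate L and an independent discontinuation rate d, both per year, with a cap T = 4.56.

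- Crude incidence = L/(L+d) × (1 − exp(−(L+d)T))
- Person-time to first event, discontinuation or cap = (1 − exp(−(L+d)T))/(L+d)
- Rate = crude incidence / person-time = L, whatever d is

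Mean exposure to discontinuation or cap is (1 − exp(−dT))/d. Worked case, L = 0.01 and d = 0.10: 0.01/0.11 × (1 − exp(−0.11 × 4.56)) = 0.0359.

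| d per year | Mean exposure (years) | Crude %, L = 0.01 | Crude %, L = 0.05 | Crude %, L = 1.0 |
|---|---|---|---|---|
| 0.10 | 3.66 | 3.59 | 16.5 | 90.3 |
| 0.20 | 2.99 | 2.93 | 13.6 | 83.0 |
| 0.50 | 1.80 | 1.77 | 8.35 | 66.6 |
| 1.00 | 0.99 | 0.98 | 4.72 | 50.0 |

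The d = 0.10 figure divided by the others:

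- L = 0.01: 1.22, 2.03 and 3.66
- L = 0.05: 1.21, 1.98 and 3.50
- L = 1.0: 1.09, 1.36 and 1.81

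In every cell the rate per patient-year equals L.

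**4. Comparison across periods of different length.** With no discontinuation and L = 0.05, crude incidence is 1 − exp(−0.05) = 4.9% over 1 year and 1 − exp(−0.05 × 4.56) = 20.4% over 238 weeks, a 4.2-fold difference at the same rate.

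**5. Change over time.** Keep d = 0.20 and let the event rate be a in year 1 and b afterwards. Crude incidence is

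a/(a+d) × (1 − exp(−(a+d))) + exp(−(a+d)) × b/(b+d) × (1 − exp(−(b+d)(T−1))).

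- Constant 0.02: 5.8%
- 0.04 falling to 0.0112: 3.56% + 2.21% = 5.8%
- 0.01 rising to 0.0244: 0.90% + 4.85% = 5.8%

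Three different risk patterns give the same percentage.

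**6. Risk window.** Ninety days is 90/365.25 = 0.246 years. As a share of time on drug plus follow-up, that is 33% after 0.5 years on drug, 20% after 1 year and 5% after 4.56 years. A rate therefore needs numerator and denominator taken from the same stated window.

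**The case against.** **A separate SAP may already hold these rates.** The amendment log says that detail on Mayo scoring was moved to a Statistical Analysis Plan, and no SAP text is in the file. This stands as a limit: the point concerns the plan as written, and such rates may exist elsewhere. The log does not mention safety analyses, so it does not show that they do.

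**The trial is descriptive and the harm lies in comparisons the plan does not make.** Section 14.4 rules out hypothesis testing, Section 14.5 speaks of incidence within each parent group, and everyone receives the same daily dose after any escalation. That is true, but a descriptive estimate still needs a denominator that can be interpreted. The failure to show change over time arises with no comparison between groups.

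**Crude is an inference.** Section 14.5 does not define incidence, and Section 14.2.1 speaks in general terms. The inference is reasonable, because counts and percentages are the only categorical summary the plan names.

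**The illustration has no anchor in the documents.** This stands. Every rate is assumed. The 3.7-fold figure needs a ten-fold difference in discontinuation between groups. The model treats discontinuation as independent of the event, which fails for AEs that lead to discontinuation.

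**The AE window is bounded and follow-up events are wanted.** Collection does end at the last visit, and Section 8.3.4 says the 90-day visit was added to capture events that may be associated with the drug. But a bound on collection is not a risk window for analysis, and the present bound includes off-drug time. Showing follow-up events separately keeps them.

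**Nothing is lost.** Dates are collected and all safety data are listed, so rates could be derived at reporting. This limits the severity; it also makes the fix cheap.

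**Conclusion.** The concern holds. As written, the plan reports AEs as percentages that depend on how long patients were observed. It does not report that length and offers no rate that allows for it. The direction is certain: at equal risk, a group with shorter exposure shows a lower percentage. The size in this trial is unknown. Under constant rates, independent discontinuation and a 4.56-year cap, the illustrated distortion runs from 1.1-fold (a common AE, modest differences in discontinuation) to 3.7-fold (a rare AE, a ten-fold difference in discontinuation). This should be changed because it bears on the first-listed objective, but it does not put the trial's data at risk. Confidence is medium, because a separate SAP may already cover it.

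**What to change.** Keep the crude tables and add to Section 14.5:

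1. Duration of exposure and total patient-years, overall and by parent-trial treatment group.
2. First-event incidence rates per 100 patient-years with 95% confidence intervals for TEAEs, SAEs, AEs leading to discontinuation and AESIs, overall and by parent group. State one risk window and use it for both numerator and denominator: for example on-treatment time, with post-treatment follow-up shown separately or as a sensitivity analysis.
3. Rates by exposure interval for SAEs and AESIs, since a constant rate may not hold over several years. Sparse intervals will be imprecise, and the confidence intervals will show it.

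If a separate SAP already specifies these analyses, align Section 14.5 with it.

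The cost is a few tables built from dose and AE dates already recorded, with no added visits or procedures for patients. The overall rate assumes a constant event rate; the interval rates check that assumption.

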7.3 Safety Endpoints

- The incidence, severity, and relationship of treatment-emergent adverse events (TEAEs), serious AEs (SAEs), TEAEs leading to discontinuation of investigational drug, AEs of special interest (AESIs), and TEAEs of special interest will be summarized.

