13.2 Adverse Events and Serious Adverse Events

13.2.1 Definition of Adverse Events

An AE is any untoward medical occurrence in a patient or clinical investigation patient administered a pharmaceutical product, which does not necessarily have a causal relationship with this treatment. An AE can therefore be any unfavorable and unintended sign (including an abnormal laboratory finding), symptom, or disease temporally associated with the use of a medicinal product, whether or not considered related to the medicinal product (ICH E2A, II.A.1).

Ulcerative colitis disease relapse and related symptoms will be monitored as trial endpoints and thus will not be recorded as AEs, unless it qualifies as a serious AE to trigger safety reporting as described in [Section 13.2.5](#).

In cases of surgical or diagnostic procedures, the condition/illness leading to such a procedure is considered as the AE rather than the procedure itself.

An Adverse Drug Reaction (ADR) is defined as all noxious and unintended responses to a medicinal product causally related to any dose (ICH E2A, II.A.2).

An Unexpected ADR is defined as an adverse reaction, the nature of which is not consistent with the applicable product information (ICH E2A, II.A.3).

Each AE is to be evaluated for duration, severity, seriousness, and causal relationship to the investigational drug. The action taken and the outcome must also be recorded.

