13.2.3 Assessment of Adverse Event Severity

The severity of the AE will be characterized as “mild, moderate, or severe” according to the following definitions:

- Mild events are usually transient and do not interfere with the patient’s daily activities.
- Moderate events introduce a low level of inconvenience or concern to the patient and may interfere with daily activities.
- Severe events are incapacitating and interrupt the patient’s usual daily activity.

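### A carried-over AE that stops extension drug without a rise in severity grade falls outside the TEAE and TEAE-discontinuation endpoints, and the plan's passages conflict on which events count

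*Combined protocol and SAP*

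**What the plan says.** Section 14.5 treats as treatment emergent any AE that starts on or after the first extension dose, and also AEs with "onset prior to the first open-label dose date in RPC01-3102 that increase in severity on or after the first dose of investigational drug". For AEs that started earlier, it says that those "which are ongoing from a previous trial to RPC01-3102, will be listed in the AE data listing and labeled as" prior events. No table is specified for them.

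Section 13.2.3 grades severity as mild, moderate or severe by effect on daily activity; at the top, "Severe events are incapacitating and interrupt the" patient's usual activity. Section 13.2.1 keeps this apart from other attributes: "Each AE is to be evaluated for duration, severity, seriousness, and causal relationship to the investigational drug". It also requires action taken and outcome to be recorded. Section 13.2.2 treats a death as the outcome of the SAE that caused it.

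The endpoint list in 7.3 names, after TEAEs, "serious AEs (SAEs), TEAEs leading to discontinuation of investigational drug, AEs of special interest (AESIs), and TEAEs of special interest will be summarized". On analysis, 14.5 says "Serious AEs and AEs leading to discontinuation will be summarized similarly", directly after the sentence that describes the TEAE tables. On data capture, 13.2.5 says of events that are already serious: "If the SAE is ongoing at the time of the first dose in RPC01-3102, it will be transcribed into the eCRF". SAEs that occur after the first dose are also entered in the extension database.

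**The concern.** Long-term safety is the first objective in 7.1. Every patient comes from an earlier RPC1063 trial, and some continue 1 mg daily without a new dose escalation. AEs that begin before entry and run on under extension drug are therefore built into the design.

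Consider a moderate AE that started in the parent trial, stays moderate, and leads to stopping drug in the extension. Under 14.5 it is a prior event, not a TEAE, so it does not meet the 7.3 endpoint of "TEAEs leading to discontinuation of investigational drug". Because the patient went on to extension dosing, it is also unlikely to have been counted as a discontinuation AE in the parent trial. That last step is inference; the documents do not state it.

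At stake are the TEAE and discontinuation incidences, which are headline results of an extension study. There is also a reproducibility problem: two programmers could build different discontinuation tables from this text and both could defend them.

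**Working it through.** The plan gives no figure to reproduce, so the check applies the 14.5 rule to the severity scale and then compares the endpoint wordings.

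**Step 1: which carried-over AEs can qualify.** With three grades at entry and three possible worst grades on extension drug there are 3 × 3 = 9 pairs. A rise is needed:

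- mild at entry: 2 of 3 pairs qualify (to moderate, to severe)
- moderate at entry: 1 of 3 (to severe)
- severe at entry: 0 of 3

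The total is 2 + 1 + 0 = 3 of 9. This counts possibilities and is not a rate, since the pairs are not equally likely. None of the qualifying conditions refers to seriousness, drug withdrawal or death. The scale has no grade above severe, so an AE that is severe at entry stays a prior event whatever follows.

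**Step 2: what each place says it will count.**

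| Place | Discontinuation events | SAEs |
|---|---|---|
| Synopsis, safety endpoints | TEAEs only | not limited to TEAEs |
| Section 7.3 | TEAEs only | not limited to TEAEs |
| Synopsis, statistical methods | AEs, no limit stated | not limited to TEAEs |
| Section 14.5 | AEs, no limit stated, but tied to the TEAE tables by *similarly* | same |

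Section 7.3 lists AEs of special interest and TEAEs of special interest side by side. The protocol thus uses AE and TEAE as different terms, and the TEAE limit on discontinuations cannot be dismissed as loose wording.

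**Step 3: result for a carried-over AE with no grade rise.**

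- TEAE incidence: left out.
- Discontinuation, by 7.3 and the synopsis endpoints: left out. By 14.5 and the synopsis methods: it may be included. The passages conflict.
- SAE summary, if the AE is or becomes serious: included by the wording in all four places. It is left out only if *similarly* in 14.5 is read as restricting the table to TEAEs.
- Fatal events: the cause of death is an SAE, so these follow the SAE line. The text specifies no separate death table.

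**Step 4: size.** Let c be the patients counted with a TEAE leading to discontinuation, and m the patients whose only discontinuation AE was carried over at an unchanged grade. The missed share is m / (c + m). The documents give neither c nor m, so no value can be put on it. The direction is fixed: m cannot be negative, so the omission can only lower the count.

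**The case against.** A reader might infer that carried-over AEs which turn serious or fatal vanish from the safety endpoints altogether. The documents do not support that. No endpoint limits SAEs to treatment-emergent ones, 13.2.2 makes the cause of a death an SAE, and 13.2.5 brings SAEs ongoing at the first dose or occurring after it into the extension database. What remains for these events is their absence from TEAE incidence and the ambiguity of one word in 14.5.

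On discontinuations, it can be argued that *similarly* refers only to layout (System Organ Class, Preferred Term, descending order), so that the 14.5 table already covers all AEs. That is a fair reading of 14.5, but it leaves the 7.3 and synopsis endpoints saying something else, so the conflict stands.

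These patients are not invisible. Carried-over AEs are listed, and 14.3 summarises non-completion by reason, with adverse event among the reasons in 9.4. This stands as far as it goes, but a disposition table gives the reason category and not the AE term, so it does not repair the AE-level count.

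The cases may also be few. An AE bad enough for hospital admission will often move up a grade and qualify, and exclusion 6 should keep out many patients with a major ongoing illness. This is plausible and bears on size; it does not change the rule.

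Finally, calling an unchanged AE emergent because drug was stopped confuses action taken with emergence. Putting a single TEAE filter on every table could also remove SAEs that are now covered. Both points are right, and the fix below avoids both.

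**Conclusion.** The point holds for TEAE incidence and for the discontinuation endpoint as worded in 7.3 and the synopsis: a carried-over AE that stops extension drug at an unchanged grade is excluded, and one already severe at entry can never become treatment emergent. Sections 7.3 and 14.5, and the two parts of the synopsis, need to be reconciled. For serious and fatal events the finding is ambiguity in the SAE tables, not established omission.

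The bias is downward and its size cannot be estimated from the documents. The conclusion assumes that a worsening AE keeps its original record and onset date, as the severity clause in 14.5 implies. If sites instead opened a new record with a new onset date, that record would count as treatment emergent. It also rests on the combined text supplied, which contains no further analysis rule that settles the matter.

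**What to change.** 1. In 7.3, the synopsis and 14.5, state that the discontinuation table counts every AE whose action taken on or after the first RPC01-3102 dose is drug withdrawn, whatever its onset date. Use one term for it in all of these places.
2. State that the SAE and death summaries count every AE that is or becomes serious, or is fatal, on or after that dose, with no treatment-emergent filter. Show SAEs that were already serious at entry and did not change in a separate row, so that transcribed events do not inflate the extension rate.
3. In the TEAE definition in 14.5, add becoming serious or fatal as alternatives to a rise in severity. Drug withdrawal need not be a trigger there, because item 1 covers it.

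Seriousness, action taken and outcome are already recorded under 13.2.1, so no new data are needed; the work is a few sentences and a programming rule. The cost is slightly less favourable rates. Because 14.6 reports that interim analyses have already been performed for regulatory submissions, a row under the current 14.5 definition should be kept for comparability.
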